# Protocol Details

## Basic Info

Confirmation Number: **djabjdjj**  
Protocol Number: **832891**  
Created By: **[name]**  
Principal Investigator: **[name]**  
Protocol Title: **Optimizing Neuromodulation through Individualized Stimulation Frequencies**  
Short Title: **Individualized Loop TMS**  
Protocol Description: Transcranial Magnetic Stimulation (TMS) is a non-invasive mechanism for stimulating the human brain. TMS can potentiate or inhibit activity in various brain regions, and it allows researchers to exert causal control over neural pathways. We will use real-time fMRI brain readout to optimize TMS delivery and measure changes in behavioral and brain response following the neuromodulation in healthy participants.  
Submission Type: **Biomedical Research**  
Application Type: **EXPEDITED Category 1**

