## **Objectives**

### **Overall objectives**

We aim to evaluate whether optimized frequency (compared to the least-optimized frequency) of excitatory TMS will generate better results in behavior and brain activity among healthy participants. Specifically, we will develop a novel tool to compute individualized multi-scale functional connectivity networks using data from baseline resting and task-evoked brain states. Building on that, we will utilize recurrent neural networks (RNN) with long short-term memory (LSTM), a promising deep learning technique, to generate brain decoding models and obtain real-time readouts of brain states. We will then establish a closed loop of rTMS and brain readouts, fine-tuning the rTMS frequency to determine the optimal stimulation frequency for each participant. Participants will receive their optimal stimulation frequency of rTMS over a three-day neuromodulation session and their least optimal stimulation frequency (the frequency least successful in moving their brain state) over another three-day neuromodulation session (order counterbalanced across subjects). We hypothesize that optimal frequency will drive performance improvements and brain changes more than the least optimal frequency.

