### **Background**

Repetitive TMS (rTMS) has been widely adopted to non-invasively stimulate the brain to improve working memory (WM) performance in both clinical and non-clinical samples (Brunoni & Vanderhasselt, 2014). However, behavioral and symptom responses to TMS remain heterogeneous and the factors governing the strength and direction of rTMS effects across individuals remain largely unknown. Accumulating evidence has demonstrated that TMS efficacy hinges upon the precision of TMS targeting, and individualized functional connectivity networks (FCNs) may help accurately identify TMS targets for individuals (Fox, Buckner, White, Greicius, & Pascual-Leone, 2012; Fox, Liu, & Pascual-Leone, 2013; Weigand et al., 2018) since effects of stimulation are propagated throughout both local and distributed brain networks (Herbsman et al., 2009; Kloppel et al., 2008). The functional brain state varies across individuals and within individuals over time (Bassett, Wymbs, Porter, Mucha, Carlson, & Grafton, 2011; Calhoun, Miller, Pearson, & Adal, 2014; Finn, Scheinost, Finn, Shen, Papademetris, & Constable, 2017), which could substantially alter the impact of TMS. Preliminary research suggests that manipulating brain states during the delivery of repetitive TMS (rTMS) neuromodulation augments the behavioral impact of rTMS (Luber et al., 2017). Through manipulation of brain state with a related behavioral task and using fMRI as the feedback signal, it may be possible to tune rTMS delivery to maximally impact the desired brain states in awake behaving study participants in a highly individualized manner. Therefore, improved efficacy of TMS could be achieved through precise TMS targeting and optimal TMS delivery tailored for individuals and optimized online based on real-time readouts of brain states. FCNs derived from functional MRI have demonstrated promising performance for identification of reproducible individualized targets. However, existing methods are limited in that they typically identify group-level functional connectivity networks (FCNs) and focus on resting state fMRI alone. Our recent work suggests that individualized, sparse, non-negative FCNs provide enhanced ability for characterizing the functional brain of individual subjects (Li, Satterthwaite, & Fan, 2017). Moreover, recent evidence suggests that task fMRI can improve upon within-subject and between-subject estimates of stable brain network representations as compared with resting state fMRI only (Finn, Scheinost, Finn, Shen, Papademetris, & Constable, 2017). Based on these findings, current study will focus on both resting and task-evoked brain states and individualized, multiscale, hierarchical functional neuroanatomy, and we will extend upon our recent published work (Li et al., 2017, 2016; Li, Zhu, & Fan, 2018) using deep matrix decomposition techniques (Trigeorgis, Bousmalis, Zafeiriou, & Schuller, 2014; Zhao, Ding, & Fu, 2017). This strategy will yield a set of individualized FCNs that share similar spatial patterns across subjects at multiple scales with a hierarchical organization,

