
facilitating individualized precise TMS targeting. Another major innovation that will facilitate optimal TMS delivery is the brain decoding for real-time online brain readouts. Recent studies have demonstrated promising brain decoding performance of prediction models built upon functional connectivity measures among FCNs within time windows with a fixed width (Shirer, Ryali, Rykhlevskaia, Menon, & Greicius, 2012; Richiardi, Eryilmaz, Schwartz, Vuilleumier, & Van De Ville, 2011). However, such fixed time windows are not likely optimal over different brain states that change at unpredictable intervals. Meanwhile, recurrent neural networks (RNNs) with long short-term memory (LSTM) (Hochreiter & Schmidhuber, 1997) have achieved remarkable advances in sequence modeling (Lipton, Berkowitz, & Elkan, 2015), and these techniques have been successfully applied to EEG and ECoG data analysis (Glaser, Chowdhury, Perich, Miller, & Kording, 2017; Schwemmer et al., 2018). Our recent study has demonstrated that brain decoding models built upon individualized FCNs using LSTM RNNs accurately decode fine-grained WM tasks and motor tasks in real time (Li & Fan, 2018). Therefore, here we will build brain decoding models to obtain real-time readouts of brain states using LSTM RNNs. Besides TMS targeting, rTMS frequency has clear neurobiological consequences successfully measured in-vivo in non-human animal brains in a landmark study (Allen, Pasley, Duong, & Freeman, 2007). Our team has adopted the interleaved TMS/fMRI technique which will allow stimulation of specific nodes while recording fMRI responses from all other brain regions (Chen et al., 2013; Fonzo et al., 2001; Nahas et al., 2001). Building on this basic strategy and the innovative methodology mentioned above, we can fine-tune the TMS frequency based on real-time feedback of TMS induced effects on the brain. Specifically, we will target FCNs identified by a brain decoding model built using LSTM RNNs, apply short trains of in-scanner rTMS, monitor the resulting brain response with fMRI, and tune TMS delivery accordingly. As a result, we can optimize noninvasive brain stimulation through individualized target and frequency. By comparing behavioral and brain responses with optimized and non-optimized stimulation frequencies, this study will provide us novel insight to variability in response to TMS and will potentially enhance the capabilities of the existing device.

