### **Design**

This study will recruit 38 healthy participants, who will be recruited through the community via study advertisements. Prior to any study visits, all subjects will be pre-screened through a phone interview with a trained member of the study team or an online self-report screening, both through REDCap. The study involves 11 study visits. The first study visit will consist of a consenting and extended screening visit. All participants will have the opportunity to ask questions before signing the electronic consent form. We will complete a semi-structured clinical interview and will demonstrate TMS to ensure the participant is comfortable with all study procedures. This visit will be completed both remote and in- person. The second study visit will involve a 1-hour MRI scan. During the scan, the participant will complete multiple computerized tasks. The MRI scan will include both structural and functional scans, and those scans will be used to localize the stimulation target for the subsequent sessions. The third study visit will be a 2-hour TMS/fMRI session, and the participant will engage in behavioral tasks while interleaved rTMS rounds are delivered at different excitatory frequencies (frequency range: 2Hz-20Hz). This scan will be used to determine the optimal stimulation frequency for the individual participant. The fourth, fifth, and sixth study visits will involve neuromodulation with either the optimized frequency or the frequency least successful in moving a participants brain state, as determined from the third study visit. Each subject will receive ~3000 pulses in each session, including the pulses from the motor threshold determination. We will determine the adjusted MT by using the Stokes equation, which accounts for differences in cortical distance from the site relative to motor cortex (where the motor threshold is found). The stimulation amplitude will be equivalent to 110% of the adjusted MT. Prior studies have safely utilized TMS with such design (VanDerwerker et al., 2018; Cristancho, Trapp, Siddiqi, Dixon, & Lenze, 2018). The seventh study visit will involve a 1-hour TMS/fMRI session while the participant is engaging in a behavioral task.. This visit is designed to examine brain and behavioral changes after the first round of neuromodulation. The seventh and the eighth visit will be scheduled at least one week apart. The eighth, ninth, and tenth study visits will mirror the fourth, fifth, and sixth study visits and will involve neuromodulation with either the optimized or least-optimized individual frequency. The order of optimized and least-optimized frequencies will be counterbalanced across participants between Visit 4-6 and Visit 8-10 (i.e., half of the participants will receive stimulations of the two frequencies in one order, and the other half will receive stimulations of the two frequencies in the reverse order). The

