## Procedures

All participants will be recruited through the University of Pennsylvania and the surrounding community. Subjects will be pre-screened for eligibility through phone or online self-report screener in REDCap. Eligible subjects will be invited in for a screening visit. Visit 1 will be a consent/ screening session. This visit will involve remote and in-person procedures. During the remote visit, a coordinator will discuss the Informed Consent Form with the participant. After going through the ICF, participants will be asked to electronically sign at the end of the ICF and complete a Remote ICF Attestation form to ensure they understood all the procedures and risk associated with the study. If they agree to participate, they will complete questionnaires related to their medical history, demographics, and eligibility to receive MRI scans and TMS. After completing the questionnaires, participants will undergo a clinical interview. This interview could be done in person or remote. If participants meet eligibility for these initial procedures, we will schedule an in-person meeting to test TMS. For the TMS demo, participants will receive several short rounds of TMS test pulses to the prefrontal cortex to ensure comfort. During this demonstration we will identify the participants resting motor threshold (MT). MT is defined as the minimum magnetic flux needed to elicit a response in a target muscle in 5 out of 10 trials. MT is the standard in the field for measuring cortical excitability and to reduce seizure risk. While TMS is usually quite tolerable, a minority of participants (20%) cannot tolerate stimulation procedures. Screening data will be recorded in REDCap; this data will be retained indefinitely until the study enrollment is completed. The information collected in this initial visit will determine if the subject meets all inclusion criteria. If participants screen-fail or withdraw, we will assign the clinical interview compensation to their virtual Greenphire Clincard. Upon meeting all criteria for inclusion in the study, subjects will then return to complete a 1-hour baseline MRI scan at Visit 2. All MRI imaging protocols will be reviewed and approved by CAMRIS. An experienced technician and a member of the study team will be present during the MR session to ensure participant safety and well-being. If the participant complains of feeling claustrophobic and does not wish to complete the MRI, the study will be terminated. Emergency personnel and equipment are immediately available to the MRI room should the need arise. It is possible that during the course of the research study, the research staff may notice unexpected findings on an MRI scan. Should this occur, the findings will be assessed by a trained radiologist. The study doctor will inform research subjects of any significant findings. Visit 3 will include fMRI and interleaved TMS/fMRI. During this scan, the participant will perform a working memory N-back task several times. Brain data from the baseline MRI scan (stimulation target in individualized brain space) will be calibrated with the skin and scalp using a Polaris Vicra camera (Brainsight neuronavigation) to allow marking of the stimulation site on a swim cap for the TMS/fMRI session. During the MRI scan, participants will receive interleaved TMS/fMRI probes to the brain targets. The purpose of this TMS/fMRI scan is to probe and modulate and measure activity in targeted neural circuits following our established methods (Chen et al., 2013). Moreover, by building brain decoding models using LSTM RNNs deep-learning technique, we can establish a closed loop of rTMS and brain readouts. As a result, we will be able to fine-tune the rTMS frequency to achieve optimal brain state and maximized working memory performance during this session. Our MRI-compatible TMS system (MagPro X100 Stimulator, MRI-B91 TMS coil) is housed in Stellar Chance (SC3T) and the Hospital of the University of Pennsylvania (HUP 6) at the 3-Tesla MRI machine. The apparatus was installed under the supervision of [name]. a member of CAMRIS. TMS in an MRI scanner involves no additional risks to the subject. Visits 4-6 will involve excitatory rTMS delivered in the

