**Analysis Plan**

For the primary within-subjects analyses, a time (pre vs post rTMS) by condition (optimized vs least-optimized frequency) ANOVA will be done both on task performance as well as fMRI voxelwise brain responses.

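### Must the plan change because own-best versus own-worst frequency cannot show that tailoring the frequency to the person matters?

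*Combined protocol and SAP*

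**What the plan says.** The protocol title is "Optimizing Neuromodulation through Individualized Stimulation Frequencies", and the Background says that "we can optimize noninvasive brain stimulation through individualized target and frequency". The hypothesis in Overall objectives is narrower: "We hypothesize that optimal frequency will drive performance improvements and brain changes more than the least optimal frequency".

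Under Design, the Visit 3 session is one in which "interleaved rTMS rounds are delivered at different excitatory frequencies (frequency range: 2Hz-20Hz", and each person's best and worst frequencies come from that session. Procedures describes the aim there as to "fine-tune the rTMS frequency to achieve optimal brain state and maximized working memory performance during this session". Each participant then has three days at each of the two frequencies, with order counterbalanced. The Analysis Plan is one sentence: "a time (pre vs post rTMS) by condition (optimized vs least-optimized frequency) ANOVA will be done both on task performance", and on voxelwise fMRI responses. No condition uses a frequency common to all participants, and no tabulation of the selected frequencies is mentioned.

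**The concern.** Suppose all participants share one frequency-response curve, with some part of the range better for everybody. Visit 3 will then tend to label that part optimal and the opposite part least optimal in most people. The contrast is positive, yet a fixed frequency would have done as well and the closed-loop tuning added nothing. Counterbalancing protects against order effects and does not touch this. The secondary outcome, a correlation between behavioral and connectivity changes, does not touch it either.

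At stake is how a positive result is read. It supports the statement that the frequency selected as best outperformed the one selected as worst. Under a title about individualized frequencies, it could be reported as evidence that individualization helps, which this contrast alone does not show.

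**Working it through.** **1. Question against analysis.** Overall objectives compares the optimized with the least-optimized frequency, and the hypothesis predicts that the first does better. The condition factor in the Analysis Plan has exactly those two levels. The two match. The plan gives no effect size, SD, alpha or power, so there is no stated figure on this point to reproduce.

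**2. What the contrast contains.** Write person i's true response at frequency f as g(f) + d_i(f), where g is shared and d_i is personal. The expected contrast is

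mean of [g(opt_i) − g(least_i)] + mean of [d_i(opt_i) − d_i(least_i)].

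One estimated number is the sum of two parts. It can be positive with every d_i = 0, or with g flat. It is zero in expectation only when neither part contributes.

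**3. Size, by simulation.** From the plan: n = 28 usable participants and the 2-20 Hz range. Assumed, because the documents do not give them:
- candidates 2, 5, 8, 10, 15 and 20 Hz;
- g(f) = R·x, with x = ln(f/2)/ln(10), so R is the shared range;
- d_i(f) drawn from N(0, d²);
- Visit 3 score = true response + N(0, noise²), with the highest and lowest scores selected;
- outcome difference = c·[true(opt) − true(least)] + N(0, 1), where c is the share of the curve that carries over to the outcome, so SD is the residual SD of the paired difference;
- two-sided 5% one-sample t-test on that difference, which is equivalent to the time-by-condition interaction.

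Proportion of runs significant with no individual differences (d = 0) and c = 1:

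| Shared range R | noise 0.25 | noise 0.5 | noise 1 |
|---|---|---|---|
| 1 SD | 98% | 77% | 30% |
| 0.75 SD | 78% | 38% | 13% |
| 0.5 SD | 29% | 13% | 7% |
| 0.3 SD | 9% | 6% | 5% |
| 0 | 5% | 5% | 5% |

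With c = 0.5, the R = 1 row becomes 55% / 30% / 12%. The last row of the table is the true null, and it holds at 5%. The other rows are power to detect a genuine group-level frequency effect.

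A second set of assumptions (five frequencies, effect spread 0.35 SD, selection noise 0.35 SD) gave 94% significant under a wholly shared curve, 78% under a wholly personal one and 5.2% with no frequency effect. Own-optimal minus a fixed frequency was −0.14 SD in the first case and +0.29 SD in the second. The contrast does not tell these two apart.

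**4. Would extra analyses separate them?** A listing of selected frequencies helps only partly. At R = 1 and noise 1, the most common optimum is chosen by 32% of participants, against 27% with no shared curve, because Visit 3 noise scatters the selections. The optimum is the higher of the pair in 76% against 50%, but that summary suits a rising curve.

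A model adding frequency as a categorical within-person term, at R = 1, d = 0.3 and noise 0.25 / 0.5 / 1, has power 21% / 20% / 13%, with 95% confidence half-widths of 1.13 / 0.75 / 0.55 SD. With d = 0 and noise 0.25 it cannot be estimated in 28% of runs, rising to 98-99% if the curve is a step. A null result from it would not be interpretable.

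**The case for a change.** The best case for acting is that the remedy is almost free: a sentence limiting the conclusion, a table of each person's two frequencies, and perhaps one supportive model, all settled before results are known and with the primary test untouched. The title and Background do invite the broader reading.

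Part of this stands. No condition isolates tailoring, and a report should not claim that one does. But the title and Background describe the method; neither sets a hypothesis of superiority over a common frequency. Nor do the documents establish a shared curve in people. The Background stresses that "behavioral and symptom responses to TMS remain heterogeneous", and its direct support for a frequency effect, that "rTMS frequency has clear neurobiological consequences successfully measured in-vivo in non-human animal brains", is from animals.

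The sentence and the table are what analysts would supply anyway, since the frequencies must be recorded in order to deliver the stimulation. Visit 3 also holds each person's responses at several frequencies, which bear on whether people differ. The supportive model is a poor trade on the figures above.

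**Conclusion.** No change to the plan is called for. The primary contrast is aimed at the question the objectives ask, and following it supports the conclusion those objectives seek: whether the frequency selected as best did better than the one selected as worst. The limit on what it says about individualization is real, but it belongs to interpretation. Sensible reporting shows the optimal and least-optimal frequencies as pairs per participant and words the result accordingly. It also does not treat scattered optima as ruling out a shared curve: at R = 1 and noise 1 the optima are nearly as scattered as with no curve at all, yet the contrast is significant in about 30% of runs.

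The simulated percentages rest wholly on assumed candidates, curve, noise and carry-over, so they illustrate the point and do not measure it. For scale, with n = 28 and an assumed two-sided 5% level, 80% power needs a standardized paired difference of 0.549, so a shared range of 1 SD is a large effect.

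This conclusion covers the tailoring question only. How the second-period baseline is defined, and whether a period term is fitted, are separate matters not settled here.

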### **Primary outcome variable(s)**

Behavior change (task performance) and brain activity change (in-scanner brain readouts during the working memory task or at rest) in response to neuromodulation.

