## **Characteristics of the Study Population**

#### **Target population**

38 healthy control participants to collect useable data from 28 healthy participants.

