#### **Accrual**

All recruitment will be conducted through the University of Pennsylvania and the surrounding community to find a total of 38 healthy participants. It is assumed that there will be some participants who screen fail, are lost to follow up, withdraw, or complete without usable scanner data. Therefore, we estimate that we will need to consent/enroll up to 38 participants overall, in order to adequately test the hypotheses on at least 28 participants.

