
same interleaved pattern at the same stimulation site as the TMS/fMRI session but with either the optimized frequency determined from that session or the frequency least successful in moving their brain state (half of the participants will receive optimized stimulation frequency, and the other half of the participants will receive least-optimized stimulation frequency during these sessions). The present study utilizes the same FDA-approved devices (Magventure Cool-Coil B65, MagVenture X100 Stimulator) to administer TMS. The TMS system is housed in the Richards Biomedical Building. Only individuals trained by the Principal Investigator ([name].) and, [name] (M.D.) will dispense TMS. In addition to receiving TMS, participants will complete questionnaires and computerized tasks during these visits. The tasks will assess reaction time, working memory, decision-making. The decision-making task will be incentive-based and the amount the participant earns will be added to their final study compensation. During some of the tasks, we may ask subjects to wear a passive eye-tracking device to record the location of your gaze at any particular time. The order of tasks will be randomized for each participant. Visit 7 will involve a 1-hour TMS/fMRI session. Participants will complete the working memory N-back task while inside the scanner. The purpose of this visit is to examine the brain and behavioral changes after the first round of neuromodulation. Visit 8-10 will mirror Visit 4-6 and will involve neuromodulation with either the optimized or least-optimized individual frequency. The order of optimized and least-optimized frequencies will be counterbalanced across participants between Visit 4-6 and Visit 8-10 (i.e., half of the participants will receive stimulations of the two frequencies in one order, and the other half will receive stimulations of the two frequencies in the reverse order). Visit 7 and the Visit 8 will be scheduled at least one week apart. In addition, unless the MRI is unavailable or we encounter scheduling constraints, Visit #3-Visit #7 will be scheduled within the same work week, such as Visit #3 is on Monday, Visits #4-7 are Tuesday/ Wednesday/Thursday, respectively, and Visit #7 is on Friday. Similarly, Visit #8-Visit #10 will be scheduled 4 work-days in a row, either Monday-Thursday or Tuesday-Friday. Visit 11 will mirror Visit 7 and examine brain and behavioral changes after the second round of neuromodulation. Monitoring will include: (1) successful recruitment, retention; (2) subject adherence; (3) safety and tolerability.

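### The behavioural primary analysis, a within-subjects ANOVA, drops participants who leave after the first round although their first-round data exist; a mixed model would keep them

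*Combined protocol and SAP*

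**What the plan says.** Task performance is a primary outcome in its own right. The Primary outcome variable(s) section lists "Behavior change (task performance) and brain activity change (in-scanner brain readouts during the working memory task or at rest"), and the hypothesis under Overall objectives is that "optimal frequency will drive performance improvements and brain changes more than the least optimal frequency".

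The Analysis Plan is one sentence. It opens "For the primary within-subjects analyses" and applies one model to both outcomes: "a time (pre vs post rTMS) by condition (optimized vs least-optimized frequency) ANOVA will be done both on task performance as well as fMRI voxelwise" data. It gives no analysis population, no missing-data rule and no handling of participants with one round only.

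Under Accrual, up to 38 people are to be enrolled "in order to adequately test the hypotheses on at least 28 participants". The losses foreseen there are screen failure, loss to follow-up, withdrawal, and completion without usable scanner data, with no split between them. The Target population section gives the same pair of numbers: "38 healthy control participants to collect useable data from 28 healthy participants".

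The Procedures section has Visit 7 examine brain and behavioural change after the first round, with the N-back done in the scanner. At least a week separates Visits 7 and 8. Visit 11 mirrors Visit 7 after the second round. Of the stimulation visits the section says: "In addition to receiving TMS, participants will complete questionnaires and computerized tasks during these visits".

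**The concern.** The time-by-condition interaction in a two-condition within-subjects ANOVA is a paired comparison: change under one frequency minus change under the other, person by person. Someone who leaves after Visit 7 has a first-round change but no second-round change, so no difference can be formed and the person is deleted. The plan names no alternative. Four further visits follow Visit 7, and the protocol itself expects withdrawals.

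Two things are at stake. The first-round data of those who leave are wasted. More importantly, the comparison is then made only in people who went through both rounds. If leaving depends on how the first round went, and is commoner after one frequency than the other, the retained sets in the two orders are selected differently. Counterbalancing the order does not undo that.

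**Working it through.** **Inputs.** From the documents: 38 enrolled, 28 usable, two orders of equal size, and 20% unable to tolerate stimulation (Procedures, in the account of the Visit 1 demonstration). Assumed, because the documents give no values: behavioural change in each round has SD 1, the correlation ρ between rounds is 0.5 or 0.7, there is no true difference, and the people who leave are exactly those with the lowest first-round change. The withdrawal rates are also assumptions.

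**The plan's own figure.** 38 − 28 = 10 expected losses, 10/38 = 26.3%. No attrition rate, effect size, alpha or power is stated, so neither number can be derived; only the difference can be checked.

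**Bias from analysing completers only.** If the lowest fraction p leaves after round 1, the mean first-round value of those who stay is m(p) = φ(z_p)/(1 − p), and their mean second-round value is ρ·m(p). The apparent first-minus-second difference is therefore (1 − ρ)·m(p).

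- m(0.1) = 0.195, m(0.2) = 0.350, m(0.3) = 0.497, m(0) = 0.

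Let condition A have the higher withdrawal rate, p_A, when it is given first, and B the rate p_B when it is first. The plan has no sequence term, so the plain paired contrast A − B pools completers in proportion to their numbers:

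bias = (1 − ρ)·[(1 − p_A)·m(p_A) − (1 − p_B)·m(p_B)] / (2 − p_A − p_B)

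| Leaving after A / B | ρ = 0.5 | ρ = 0.7 |
|---|---|---|
| 10% / 10% | 0 | 0 |
| 20% / 0% | 0.5 × (0.8 × 0.350)/1.8 = 0.078 | 0.047 |
| 30% / 10% | 0.5 × (0.7 × 0.497 − 0.9 × 0.195)/1.6 = 0.054 | 0.032 |

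The false advantage goes to the condition with more withdrawals.

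**Set against sampling error.** The standard error of the paired contrast with 28 participants is √(2(1 − ρ)/28): 0.19 SD at ρ = 0.5 and 0.15 SD at ρ = 0.7. The largest bias above is 0.078/0.189 = 0.41 of a standard error.

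**Does a mixed model remove it?** Leaving depends here only on the observed first-round value, so a likelihood-based model that keeps the one-round participants should be unbiased. Simulating both unequal-withdrawal scenarios at both correlations, with 1,000,000 people per order, a model with condition, period and sequence gave a bias below 0.001 SD. The period term is needed. One-round participants contribute only first-round data, so a difference between rounds, such as practice, leaks into the condition effect when withdrawal is unequal. With an assumed shift of 0.4 SD between rounds, omitting period left 0.03 to 0.04 SD of bias.

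**Precision gained.** Take 28 completers (14 per order) plus 5 first-round-only participants (2.5 per order on average). The per-order variance falls from 2(1 − ρ)/14 to (1 − ρ)²/16.5 + (1 − ρ²)/14. At ρ = 0.5 that is from 0.0714 to 0.0687, equivalent to 28 × 0.0714/0.0687 = 29.1 complete pairs. At ρ = 0 it is 30.3, and at ρ = 0.7 it is 28.7.

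**How many records might be at issue.** If the 20% intolerance applied to all 38 and fell entirely at screening, 0.20 × 38 = 7.6 of the 10 losses would have no outcome data, leaving about 2 people. Because the losses are not split by reason, the documents bound the number only between 0 and 10.

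**The case against.** The strongest objection concerns a reading that is tempting but unsupported. Because the usable number is reached partly by removing people without usable scanner data, a reader might infer that participants with spoiled images will be excluded from the behavioural analysis too. No section says so. Accrual and Target population are recruitment targets, the figure of 28 is a minimum, and the Analysis Plan mentions no scan filter. The documents are silent on who enters the behavioural analysis; they do not state an exclusion. Nor is the N-back wholly independent of scanning: it is done in the scanner at Visit 7, so an aborted session would lose it, while poor images alone would not. The working-memory tasks at the non-scan visits are not named as the primary behavioural measure.

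The bias figures can also be challenged. Nothing in the documents suggests that paid healthy volunteers leave because of poor performance, or more often after one frequency. Removing exactly the lowest performers is an extreme rule. With about 30 people stimulated, the two unequal scenarios lose about 3 and 6 of them and leave fewer than the planned 28. All this stands, and the figures should be read as an upper illustration.

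What the objection does not touch is the deletion of one-round participants. That follows from the stated method.

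**Conclusion.** The point holds for withdrawal. The stated ANOVA, in its conventional form, confines the behavioural comparison to people who complete both rounds, although the protocol measures behaviour after one round and expects some people to leave. The possible bias is about 0.08 SD (20% versus 0% leaving) or 0.05 SD (30% versus 10%) at a correlation of 0.5, and less at 0.7. It is zero if withdrawal is equally frequent and equally related to outcome after both frequencies. These sizes rest on assumed rates and a worst-case leaving rule, and all are below one standard error. The precision gain is modest: five one-round participants are worth about one extra pair at a correlation of 0.5.

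On scan quality the conclusion is narrower: one usable number, partly conditioned on scanner data, serves both primary outcomes, and the behavioural set is left undefined. The change is worth making because it is cheap and settles who is analysed before results are seen. The likely numerical effect is small.

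**What to change.** In the Analysis Plan, analyse task performance with a linear mixed model: a random effect for participant and fixed effects for time, condition, their interaction, period and sequence. If pre and post scores are modelled rather than change, add period by time, so that a first-round practice gain is not credited to a condition. Include every stimulated participant with task data from at least one round, regardless of image quality. Keep the both-rounds-complete ANOVA as a sensitivity analysis. For the brain outcome, include scans that meet quality thresholds fixed in advance.

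Under Accrual, state that 28 is the target for the brain outcome. Report withdrawals, with reasons, by round and by the condition just received.

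This costs wording only: no extra visits, data or participants. The one drawback is that the two primary outcomes will have different denominators, which the report should state.
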